## **7 ASSESSMENT OF EFFICACY**

### **7.1 Efficacy Variables**

Efficacy variables include:

- Proportion of patients who experienced at least one system-generated error based on the Controller data while using the Zalviso System
- Proportion of patients, if any, with tablet dispensed but not requested
- Proportion of patients, if any, with tablet dispensed when the Zalviso System is in lockout
- Proportion of patients with misplaced tablet(s)
- Number of misplaced tablets (i.e., tablet found outside the patient’s mouth)
- Proportion of patients who experienced either a system-generated error or a misplaced tablet (i.e. a dispense failure)
- Assessment of the number of Zalviso System notifications to the nurse to retrain patient to not pull down on Controller while dosing (i.e., mitigation of Error 302)
- Proportion of patients who rate the Patient Global Assessment (PGA) of method of pain control over 24, 48 and 72 hours as “good” or “excellent”
- Proportion of patients who responded in each category of the PGA
- Proportion of Healthcare Professionals who rate the Global Assessment (HPGA) of method of pain control over 24, 48 and 72 hours as “good” or “excellent”
- Proportion of Healthcare Professionals who responded in each category of the HPGA
- Proportion of patients who terminate from the study due to inadequate analgesia over the 24-hour, 48-hour and 72-hour study period
- Time-weighted summed pain intensity difference (SPID) over the 24-hour study period (SPID24), over the 48-hour study period (SPID48), and over the 72-hour study period (SPID72)
- Total pain relief (TOTPAR) over the 24-hour study period (TOTPAR24), over the 48-hour study period (TOTPAR48) and over the 72-hour study period (TOTPAR72)
- Pain intensity (PI) at each evaluation time point
- Pain intensity difference (PID) at each evaluation time point
- Pain relief (PR) at each evaluation time point
- Patient Usability Questionnaire (PUQ)
- Nurse Usability Questionnaire (NUQ)
- Total number of study drug doses used over 24, 48, and 72-hour study period, average hourly use, and average inter-dosing interval.

- Total amount of supplemental morphine utilized

## **8 ASSESSMENT OF SAFETY**

### **8.1 Safety Variables**

Safety assessments will include the assessment of adverse events, vital signs (blood pressure, heart rate and respiratory rate), oxygen saturation, and the use of concomitant medications.

#### **8.1.1 Physical Examination/Vital Signs**

The physical examination will include examination of general appearance, skin, neck (including thyroid), eyes, ears, nose, throat, oral mucosa, heart, lungs, abdomen, lymph nodes, extremities, and nervous system. Height and weight will be measured.

Vital signs will include respiratory rate, radial pulse rate, and systolic and diastolic blood pressures. The patient may be sitting, semi-recumbent or lying down. Recordings are to be made after the patient has been in the same position for 5 minutes or more and the position will be recorded. Heart rate will be measured over 30 seconds and respiratory rate will be measured over 1 minute.

Respiratory rate and other vital signs may be checked at additional times on an ad hoc basis per the judgment of the study staff. Oxygen saturation (SpO2) will be measured continuously by pulse oximetry but will only be recorded at the time points when respiratory rates are measured and recorded.

#### **8.1.2 Laboratory Parameters**

A urine drug of abuse screen (barbiturates, benzodiazepines, cocaine, marijuana, phencyclidine, and opiates) will be performed at screening. A test for pregnancy will be done at screening and after admission to the hospital for women who are of childbearing potential.

#### **8.1.3 Adverse Events**

An adverse event is any illness, sign, laboratory value or symptom which appears or worsens during the clinical trial, regardless of causal relationship to the investigational drug. AEs that occur from the first dose of study drug and for 12 hours after the last dose of study drug will be documented on the AE CRF. The Investigator will assess the AE severity and relationship of the AE to study drug. The Investigator will treat the patient as medically required until the AE either resolves or becomes medically stable. Treatments and medications required to treat AEs will be recorded on the appropriate pages of the CRFs.

##### **8.1.3.1 Adverse Event Severity is Defined as Follows:**

*Mild:* The event may be noticeable to the patient, but does not influence the patient's daily activities. The event usually does not require special treatment.

*Moderate:* The event may result in slight discomfort for the patient and performance of the patient's daily activities may be influenced. The event may require intervention.

*Severe:* The event may result in severe discomfort for the patient and usually interferes with the patient's daily activities. The patient may not be able to continue in the study and treatment or other intervention is usually needed.

#### **8.1.3.2 Adverse Event Relationship to Study Drug is Defined as Follows:**

*Probably related:* Study drug administration and AE occurrence are reasonably related in time; AND, the AE is more likely explained by exposure to study drug than by other mechanisms.

*Possibly related:* Study drug administration and AE occurrence are reasonably related in time; AND, AE is explained equally well by causes other than study drug.

*Not related:* AE is obviously explained by another cause; OR, the time of occurrence of AE is not reasonably related to administration of the study drug.

#### **8.1.3.3 Serious Adverse Events**

Serious, life-threatening, and unexpected AEs will be identified and handled in accordance with the guidelines specified in the US Code of Federal Regulations (CFR).

A serious adverse event (SAE) is defined as any event that is fatal or life-threatening, permanently or substantially disabling or incapacitating (causing a substantial disruption of a person's ability to conduct normal life functions), prolongs hospitalization, a congenital anomaly, or an important medical event. Important medical events are defined as events that may not result in death, be life threatening, or prolongs hospitalization but, based on appropriate medical judgment, may jeopardize the patient and may require medical or surgical intervention to prevent one of the outcomes listed in the definition of an SAE.

A life-threatening AE is one that, in the view of the Investigator, places the patient at immediate risk of death from the reaction as it occurred.

An unexpected AE is any event, for which the specificity or severity is not consistent with the AE profile in the current package insert for Sufenta (Appendix VI) or the Zalviso System Investigator Brochure.

All SAEs, regardless of cause(s) or relationship to study drug, must be reported immediately to AcelRx or designee. Additional contact numbers and AE/SAE reporting instructions will be provided to each site in a separate document.

The name of the Medical Monitor and contact information will be provided to each study site.

The Investigator must report via phone or fax an SAE within 24 hours of learning of the event. The investigator must complete the Serious Adverse Event Report Form and

submit it along with other relevant pages of the CRF within 1 working day to AcelRx or its designee. The Investigator will also compile with urgent priority other relevant documentation (e.g., copies of test results, hospital discharge summary, autopsy report, etc.) and send this information to AcelRx or its designee. All SAEs will also be reported on the AE page of the CRF, and concomitant medications administered in association with the SAE will be documented on the Concomitant Medication page of the CRF.

Regulatory agencies and all participating Investigators will be notified in writing of any SAE that is both associated with the use of the study drug and unexpected within 15 calendar days from when the SAE was reported to AcelRx or safety designee. Safety reporting shall also include events described in the scientific literature. Regulatory agencies will be notified by telephone or fax within 7 calendar days of any unexpected fatal or life-threatening AE associated with the use of the study drug.

AEs and SAEs that occur during the study treatment period will be documented. Any SAEs reported during the 30 days after the last dose of study drug will be reported and captured in the CRF.

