#### *Safety Assessments*

The patient will be monitored continuously by a study staff member for the first hour following the first dose of study drug.

Heart rate and blood pressure will be recorded prior to administration of the first dose of study drug, and when pain intensity and pain relief assessments are made i.e. 15, 30, and 45 minutes, and 1, 2, 4, 6, 8, 10, and 12 hours after the first on-demand dose. Blood pressure and heart rate will then be measured every four hours during the 12 to 72 hour

study period. During the first 24 hours of treatment, respiratory rate and oxygen saturation will be recorded prior to the first dose of study drug, 15,30, 45, and 60 minutes after the first dose of study drug, and then every 30 minutes. During the 24 to 72 hour study period, the respiratory rate and oxygen saturation will be recorded every 2 hours.

When vital signs are to be measured at the same time as PI and PR scores, the vital sign measurements may be taken up to 5 minutes before the scheduled time, in order for PI and PR scores to be self-recorded by patient at the scheduled time.

The Investigator or the Medical Monitor may exercise his/her judgment to terminate a patient's participation in the study due to clinically significant changes in any clinical parameter.

Patients will be instructed to report any AEs they experience throughout the duration of the study. Reported AEs and any concomitant medications administered during the study period will be recorded in the CRF. SAEs that occur within 30 days of the last dose of study drug will be reported.

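### The printed SAE definition has no criterion for a new hospital admission, so in the 30-day SAE window a readmission after discharge is reportable only if it meets some other criterion

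*Protocol*

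**What the plan says.** Protocol 8.1.3.3 defines an SAE by a closed list: fatal or life-threatening, permanently or substantially disabling, then "prolongs hospitalization, a congenital anomaly, or an important medical event". Important medical events are then explained as "events that may not result in death, be life threatening, or prolongs hospitalization" which, as judged clinically, "may jeopardize the patient and may require medical or surgical intervention to prevent one of the outcomes listed in the definition of an SAE". Neither sentence mentions a new admission.

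The SAE window is stated twice. Under Safety Assessments in Protocol 6.1.3: "SAEs that occur within 30 days of the last dose of study drug will be reported". At the end of 8.1.3.3: "Any SAEs reported during the 30 days after the last dose of study drug will be reported and captured in the CRF". For adverse events generally the window is much shorter: Protocol 8.1.3 has the AE form cover "AEs that occur from the first dose of study drug and for 12 hours after the last dose of study drug".

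The patients are postoperative in-patients (Synopsis), and treatment lasts 24 to 72 hours (Protocol 3.5). SAP 2.11.3 tabulates SAEs in Table 14.3.5 but gives no definition of its own.

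**The concern.** Prolongation works as a criterion while the patient is still in the index stay. After discharge an admission starts a new stay and prolongs nothing, so the criterion stops operating for any part of the 30-day window that falls after discharge.

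Two things are at stake. The first is whether the SAE table is complete for the period that the protocol itself chose to cover. The second is consistency: if reporting a readmission depends on whether a site calls it an important medical event, the same event can be an SAE at one site and go unrecorded at another. The general AE form is no safety net, because it closes 12 hours after the last dose.

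**Working it through.** There is no planned figure to reproduce. The check sets the definition against the two collection windows.

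**Inputs**
- Hospitalization criterion: prolongation only, in both sentences (Protocol 8.1.3.3).
- SAE window: 30 days after the last dose (Protocol 6.1.3 and 8.1.3.3, in agreement).
- General AE window: first dose to 12 hours after the last dose (Protocol 8.1.3). SAP 2.11.2 uses the same 12 hours for its on-treatment AE summary.
- Date of discharge and readmission rate: not given in either document.

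**Step 1. Length of the period with SAE-only capture.** Both windows are counted from the last dose, so they subtract directly:

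12 hours = 0.5 day; 30 − 0.5 = 29.5 days; 29.5 / 30 = 98.3%.

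For 29.5 of the 30 days, a new event is recorded only if it meets the SAE definition.

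**Step 2. A readmission in that period, taken through the printed list.**

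| Criterion in 8.1.3.3 | Does a readmission as such meet it? |
|---|---|
| Fatal or life-threatening | Only if the event itself is |
| Disabling or incapacitating | Only if the event itself is |
| Prolongs hospitalization | Not after discharge, as no stay is in progress |
| Congenital anomaly | No |
| Important medical event | Only if the investigator so judges |

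The last row is the only route open to a readmission that is not otherwise severe. It is tied to preventing one of the listed outcomes, and admission is not a listed outcome.

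**Step 3. Is the criterion supplied elsewhere?** No other section of the protocol, and nothing in the SAP, adds a new-admission criterion.

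**Step 4. Result.** An event that begins more than 12 hours after the last dose, leads to readmission and meets none of the other criteria is recorded neither as an SAE nor as an AE. An event that began within the 12 hours would be on the AE form, but a later admission would not by itself make it serious under the printed list.

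**The case against.** The strongest reply is that sites do not work from the printed list alone.

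- **Federal regulations.** The opening sentence of 8.1.3.3 refers both the identification and the handling of serious events to the US Code of Federal Regulations. That is more than a remark about procedure. But the regulatory text is not reproduced, and the section then prints an explicit definition that a site can be expected to apply.
- **Separate instructions.** The section says that "AE/SAE reporting instructions will be provided to each site in a separate document", and sites also complete an SAE report form. These may include admission as a criterion. They are not available for review; if they do include it, they differ from the protocol, which should still be aligned.
- **Important medical events.** This clause will catch many grave readmissions. It stands as partial cover, but it rests on site judgement.

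Three stronger readings are tempting and are not supported.

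- **Share of the window after discharge.** A reader might subtract the 24 to 72 hours of treatment from the 30 days and conclude that 27 to 29 days fall after discharge. The window starts at the last dose, so treatment time is not inside it. The relevant interval, last dose to discharge, is not stated.
- **Frequency.** A reader might infer that readmission is the commonest serious event after discharge. Neither document gives a rate.
- **Expedited reporting.** A reader might infer a broad failure here. The 15-day reports cover only SAEs that are both drug-associated and unexpected. Protocol 8.1.3.2 classes an event with implausible timing as not related, and Protocol 1.2 gives a sublingual context-sensitive half-time of 2.5 hours, so late readmissions would seldom qualify. Fatal and life-threatening events are already in the definition. What stands is narrow: a readmission that never reaches the sponsor is not assessed for these conditions.

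**Conclusion.** The omission is real, and it appears in both sentences that mention hospitalization. Under the printed list, for 29.5 of the 30 days of SAE collection, a newly arising readmission that is not fatal, life-threatening or disabling depends on being judged an important medical event; otherwise it is recorded nowhere. The regulatory reference, the unseen site instructions and the important-medical-event clause reduce this exposure without removing it.

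The conclusion assumes that many patients are discharged within the 30 days. That is reasonable after 24 to 72 hours of treatment, but it is not stated. The number of readmissions affected cannot be estimated from the documents.

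The consequence is mainly for the completeness and between-site consistency of Table 14.3.5, with a limited effect on expedited reporting of drug-associated, unexpected events. Sample size, power and the device dispense failure analysis are unaffected. The change should be made because the rule, followed as printed, gives an incomplete safety record and is easy to correct.

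**What to change.** In both sentences of Protocol 8.1.3.3, replace the prolongation-only wording with *requires inpatient hospitalization (including readmission) or prolongs existing hospitalization*. Align the SAE report form and the separate site instructions with it.

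The cost is a wording change communicated to sites and a few more SAE reports. It adds no visit, contact or analysis.

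Its reach is limited. The protocol schedules no contact after the end-of-study procedures, so the new wording captures only those readmissions that the site learns of.

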## **9 STATISTICAL METHODS AND DATA ANALYSIS**

### **9.1 Determination of Sample Size**

This is a multicenter, open-label, single treatment clinical study designed to evaluate the overall functionality of the Zalviso System (sufentanil sublingual tablet system) 15 mcg for the treatment of acute moderate-to-severe postoperative pain. A sample size of approximately 330 patients is planned for this study in order to have at least 315 patients receive study drug and have available efficacy data for data analysis.

A sample size of 315 patients will have 90% power to demonstrate that the device dispense failure rate is non-inferior to a target of 2%. This failure rate is the proportion of patients who experienced at least one of following events: (1) a system-generated error, (2) a tablet dispensed but not requested, or (3) a tablet dispensed when the Zalviso System is in lockout. All events listed above will be obtained from the Controller patient usage data.

This is based on the criteria that the upper limit of a 90% confidence interval (CI) of the device dispense failure rate is not worse than 5%. This calculation is based on the exact binomial test of one-sample proportion for a one-sided case against a 2% target proportion with a delta of 3%, and a one-sided significance level of  $\alpha=0.05$ . This sample size was generated from the SAS procedure PROC POWER for one-sample proportion. Exact power computations are based on the binomial distribution and computing formulas provided by Johnson and Kotz (1970). Assuming a 5% non-evaluable rate, a sample size of 330 patients is planned for this study.

## **9.2 Tests of Hypothesis and Significance Levels**

Both continuous and categorical efficacy variables will be summarized descriptively. A point estimate of the device dispense failure rate and its 90% confidence interval based on the exact binomial test will be constructed.

## **9.3 Randomization and Blinding of the Treatment Assignment**

This is an open-label single treatment study. There is no randomization of patients or blinding of treatment. Patients who meet the eligibility requirements will be enrolled into this study sequentially within each study center to receive study treatment.

## **9.4 Baseline Comparability**

Demographics and baseline characteristics will be summarized by sex group for all enrolled patients and all patients received study drug. Data will be pooled for all study centers for the descriptive summary of baseline data. No formal hypothesis testing will be performed for baseline data.

## **9.5 Analysis of Efficacy Data**

Sections related to the analysis of efficacy data are specified below by topic.

### **9.5.1 Efficacy Variables and Parameters**

The efficacy variables and parameters are:

1. Proportion of patients who experienced at least one system-generated error based on the Controller data while using the Zalviso System
2. Proportion of patients, if any, with tablet dispensed but not requested
3. Proportion of patients, if any, with tablet dispensed when the Zalviso System is in lockout
4. Proportion of patients with misplaced tablet(s)
5. Number of misplaced tablets (i.e., tablet found outside the patient's mouth)
6. Proportion of patients who experienced either a system-generated error or a misplaced tablet (i.e. a dispense failure)
7. Assessment of the number of Zalviso System notifications to the nurse to retrain patient to not pull down on Controller while dosing (i.e., mitigation of Error 302)
8. Proportion of patients who rate the Patient Global Assessment (PGA) of method of pain control over 24, 48 and 72 hours as "good" or "excellent"
9. Proportion of patients who responded in each category of the PGA
10. Proportion of Healthcare Professionals who rate the Global Assessment (HPGA) of method of pain control over 24, 48 and 72 hours as "good" or "excellent"
11. Proportion of Healthcare Professionals who responded in each category of the HPGA
12. Proportion of patients who terminate from the study due to inadequate analgesia over the 24-hour, 48-hour and 72-hour study period
13. Time-weighted summed pain intensity difference (SPID) over the 24-hour study period (SPID24), over the 48-hour study period (SPID48), and over the 72-hour study period (SPID72)

14. Total pain relief (TOTPAR) over the 24-hour study period (TOTPAR24), over the 48-hour study period (TOTPAR48) and over the 72-hour study period (TOTPAR72)
15. Pain intensity (PI) at each evaluation time point
16. Pain intensity difference (PID) at each evaluation time point
17. Pain relief (PR) at each evaluation time point
18. Patient Usability Questionnaire (PUQ)
19. Nurse Usability Questionnaire (NUQ)
20. Total number of study drug doses used over 24, 48, and 72-hour study period, average hourly use, and average inter-dosing interval.
21. Total amount of supplemental morphine utilized

### **9.5.2 Analysis Population and Handling of Dropouts**

The main analysis of the efficacy variables will include the intent-to-treat (ITT) population. The ITT population includes enrolled patients who received study drug.

For patients missing PI or PR data, the following methods will be applied to impute the missing data at evaluation time points for the duration of study period:

- (1) Missing data will be first imputed on a patient-by-patient basis by linear interpolation method between two observed pain scale values.
- (2) Data occurring after a patient terminated from study or did not provide any follow-up data after last available data prior to the end of study period, the pain scale values at follow-up time points post-termination up to the end of the study period will be imputed on a patient-by-patient basis as described below.

The last observation carried forward (LOCF) method will be used to impute any remaining missing data points after termination due to reasons other than adverse event up to the end of the study period. For patients who prematurely terminated from the study due to adverse event, the worst observation carried forward (WOCF) method will be used to impute the remaining missing data points up to the end of the study period. The worst PID is the smaller number between number zero and the last PID obtained prior to termination. The worst PR is number zero.

For patients who used any supplemental opioid during the study period, the last observed pain intensity prior to using each dose of supplemental opioid will be carried throughout a follow-up 1-hour time interval. Any pain intensity collected within 1 hour after the start of any supplemental opioid will be excluded from the calculation of the time-weighted SPID24. This same imputation method will also be used to calculate the efficacy endpoints derived from pain assessment data.

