### **3.3 Blinding and Randomization**

This is an open-label single treatment study. There is no randomization in this study. All patients will receive treatment using the Zalviso System.

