### **5.4 Managing Suspected Zalviso System Errors and Failures**

Refer to the Healthcare Professional-Instructions for Use (HP-IFU) for complete information on Zalviso System alarm, error and notification messages (HP-IFU to be sent under separate cover).

If during patient use an error message is displayed on the controller screen (e.g., Error 301, Error 302, etc), the error displayed will be recorded in the source record and on the suspected technical failure e-CRF. Per the Zalviso System design, if a system error occurs, the Zalviso System will no longer dispense tablets and must be discontinued. The patient will be discontinued from the study and alternate form of postoperative analgesia per standard practice at the site should be instituted.

If either the patient or the investigator's staff observes that the Zalviso System may not be operating properly during patient use, but there are no notification or error messages displayed on the Zalviso System Controller screen, the Zalviso System will be evaluated for the presence of a technical failure in accordance with the procedures detailed in the Zalviso System HP-IFU. If the Zalviso System is suspected of having a technical failure, the System must be discontinued, the patient discontinued from the study and an alternate form of postoperative analgesia per standard practice at the site should be instituted. In the event any Zalviso System is judged to have a suspected technical failure, the Zalviso System will be sent to AcelRx for evaluation and may not be used further until a review by AcelRx is complete and the System is approved for further use. Suspected technical

failures must be documented in the source and the eCRF.

If a misplaced tablet (i.e. any tablet inadvertently dispensed or found outside of the patient's mouth) is found by a patient or study staff, this must be documented in the source record and eCRF. The tablet must be stored securely until CII study drug accountability is conducted. The study staff should document who found the tablet, when and where the tablet was found, and query the patient to determine the likely cause of the misplaced tablet.

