2.10.2 Analysis Population and Handling of Dropouts

All enrolled patients are those who are enrolled and receive the study treatment. The main analysis of efficacy endpoints includes all enrolled patients.

For patients missing PI or PR data, the following methods will be applied to impute the missing data at evaluation time points for the duration of study period:

- (1) Missing data will be first imputed on a patient-by-patient basis by linear interpolation method between two observed pain scale values.
- (2) Data occurring after a patient terminated from study or did not provide any follow-up data after last available data prior to the end of study period, the pain scale values at follow-up time points post-termination up to the end of the study period will be imputed on a patient-by-patient basis as described below.

The last observation carried forward (LOCF) method will be used to impute any remaining missing data points after termination due to reasons other than adverse event up to the end of the study period. For patients who prematurely terminate from the study due to adverse event, the worst observation carried forward (WOCF) method will be used to impute the remaining missing data points up to the end of the study period. The worst PID is the smaller number between number zero and the last PID obtained prior to termination. The worst PR is number zero.

For patients who use any supplemental opioid during the study period, the last observed pain intensity prior to using each dose of supplemental opioid will be carried throughout a follow-up 1-hour time interval. Any pain intensity collected within 1 hour after the start of any supplemental opioid will be excluded from the calculation of the time-weighted SPID. This same imputation method will also be used to calculate the efficacy endpoints derived from pain assessment data.

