2.11 Analysis of Safety Data

The safety data collected in this study include:

- (1) Adverse events(AEs)
- (2) Pregnancy test results
- (3) Vital signs
- (4) Physical examination data
- (5) Suspected technical failures
- (6) Concomitant medications

All enrolled patients who receive at least one dose of study drug will be included in the analyses and summaries of safety data.

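### On its most natural reading, Protocol 9.5.2 leaves a system error on the first attempted dose, with no tablet delivered, out of the device dispense failure rate, and SAP 2.10.2 does not settle the case

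*Protocol*

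**What the plan says.** **Event.** Protocol 9.1, repeated in SAP 2.1, defines a device dispense failure as at least one of three events: "1) a system-generated error, (2) a tablet dispensed but not requested, or (3) a tablet dispensed when the Zalviso System is in lockout". All three are to be taken from the Controller data. Variable 1 in Protocol 9.5.1 counts patients with "at least one system-generated error based on the Controller data while using the Zalviso System". Neither definition requires a delivered tablet.

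**Consequence of an error.** Protocol 5.4 states that "if a system error occurs, the Zalviso System will no longer dispense tablets and must be discontinued", and the patient leaves the study. Its instruction to record errors begins "If during patient use an error message is displayed on the controller screen", so an error on a first attempt is within its scope.

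**Population, Protocol.** Section 9.5.2 assigns the main analysis of efficacy variables to the ITT population: "The ITT population includes enrolled patients who received study drug". Section 9.5.4 treats the device dispense failure results as efficacy data and names no other population.

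**Population, SAP.** Section 2.10.2 says "All enrolled patients are those who are enrolled and receive the study treatment" and analyses all of them. Study treatment is not defined there. For safety, SAP 2.11 is worded differently: "All enrolled patients who receive at least one dose of study drug will be included in the analyses and summaries of safety data". Protocol 3.3 describes treatment in terms of the device: "All patients will receive treatment using the Zalviso System".

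**Criterion.** The upper limit of the 90% confidence interval for the failure rate must be no worse than 5% (Protocol 9.1, SAP 1).

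**The concern.** Consider a patient who is enrolled, is given the System, attempts a first dose and gets an error with no tablet. Under 9.1 this is a failure. Under 5.4 no tablet follows. If 9.5.2 means that a tablet must have been received, the patient drops out of both numerator and denominator. Membership of the analysis set would then depend on the outcome being measured, and every patient lost in this way is a failure, so the error can run in only one direction. It affects the trial's first listed objective and its only pass/fail criterion.

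Because the SAP wording allows either reading, the choice could also be made after the Controller data are seen. Errors after a first tablet are not at issue. Those patients received drug and are counted.

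**Working it through.** **1. Reproduce the design.** Inputs from Protocol 9.1: n = 315, limit 5% (2% target plus delta 3%), assumed true rate 2%, one-sided alpha 0.05. SAP 2.10.4 specifies the exact Clopper-Pearson interval. The largest count c with P(X ≤ c | n = 315, p = 0.05) ≤ 0.05 is c = 9.
- P(X ≤ 9 | p = 0.05) = 4.5%, the chance of a false pass.
- P(X ≤ 9 | p = 0.02) = 89.6%, which agrees with the stated 90% power.
- The limit of 9 events holds for every n from 311 to 335, which covers the planned 315 to 330. At n = 330 the two figures are 3.1% and 87.1%.

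**2. Effect of omitted patients.** The upper limit for x events in n is the 95th percentile of Beta(x + 1, n − x). Each omitted patient adds one to both x and n.

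| Counted | Upper limit | With omitted patients added | Upper limit |
|---|---|---|---|
| 9/315 | 4.93%, pass | 10/316 (one) | 5.31%, fail |
| 8/315 | 4.54%, pass | 10/317 (two) | 5.29%, fail |
| 6/315 | 3.7%, pass | 9/318 (three) | 4.89%, pass |
| 6/315 | 3.7%, pass | 10/319 (four) | 5.26%, fail |
| 9/330 | 4.71%, pass | 10/331 (one) | 5.07%, fail |

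The expected count at a 2% rate is 315 × 0.02 = 6.3, so the planned result can absorb three omissions.

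**3. How many might be omitted.** The documents give no figure, so this step is an illustration. Assume that every failure is a system error, that the risk per dose is constant, and that an error on the first attempt delivers no tablet. Protocol 1.1 describes 40 tablets as about a two-day supply, or about 20 doses a day: k = 20, 40 and 60 doses by 24, 48 and 72 hours. The share of failures falling on the first attempt is s = [1 − (1 − p)^(1/k)]/p, about 5%, 2.5% and 1.7%.
- Expected omissions at p = 2%, n = 315: 315 × 0.02 × s = 0.32, 0.16 and 0.11.
- At p = 5% and s = 5%: 315 × 0.05 × 0.05 = 0.79.

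**4. Effect on the false-pass chance.** The rate among treated patients is p(1 − s)/(1 − ps). At p = 5% and s = 5% this is 0.0475/0.9975 = 4.76%. P(X ≤ 9) at a true 5% rate is then:

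| Share s | 315 treated | 330 treated |
|---|---|---|
| 0 (all counted) | 4.5% | 3.1% |
| 1.7% | 5.1% | 3.5% |
| 2.5% | 5.4% | 3.8% |
| 5% | 6.5% | 4.6% |
| 10% (assumed, not from constant risk) | 9.3% | 6.8% |

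The last row is included because the Protocol links Error 302 to pulling down on the Controller while dosing. Handling errors of that kind could cluster on early attempts, but the documents do not say that they do.

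**The case against.** **The Protocol wording may not be as strict as it looks.** Section 9.6 asks for one dose or more of study drug for safety, while 9.5.2 asks only that study drug was received. If a difference in phrasing makes the SAP ambiguous, the same argument applies to the Protocol. This stands in part. The Protocol generally uses study drug for doses taken, so the narrow reading remains the more natural one, but a reader who infers that exclusion is certain goes further than the text does.

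**The SAP leans toward inclusion.** SAP 2.9 tabulates all enrolled patients and, separately, the safety population, and SAP 2.11 starts from enrolled patients and then adds a dose requirement. If treatment already meant a dose, both would be redundant. SAP 2.7 also refers to a table defining the populations, which is not in the documents. This stands, and for that reason a reader should not infer that the SAP makes the same exclusion or that the two documents flatly contradict each other.

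**The link from 9.5.2 to the primary rate is inferred.** The three-part composite is not itself in the 9.5.1 list. That is true, but its components are, and 9.5.4 calls the results efficacy data.

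**The event is hypothetical and small.** No section says that an error can precede the first tablet. This stands and limits the weight of the point. It does not remove the case for settling the rule in advance, because the wording costs almost nothing.

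**Conclusion.** A minor point that holds. On its most natural reading, Protocol 9.5.2 omits a failure that 9.1 counts, and SAP 2.10.2 leaves the case open. Any resulting bias favours the device. It changes the conclusion only near the limit of 9 events; at the expected 6/315, three omissions would not matter. Under constant risk per dose, the expected number omitted at the planned 2% rate is 0.11 to 0.32 patients (n = 315), and it may be zero.

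A reader might infer that the false-pass risk is materially inflated. The documents do not support that. They give no frequency for first-attempt errors. Under constant risk the chance rises from 4.5% to between 5.1% and 6.5% with 315 treated patients, and stays below 5% with 330. The higher figures need an assumed first-attempt share of 10%. The stated sample size and power are unaffected.

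**What to change.** In Protocol 9.5.2 and SAP 2.10.2, define one analysis set for all device-performance endpoints: the primary device dispense failure rate, its three components, misplaced tablets, and variable 6 (system error or misplaced tablet). The set is all enrolled patients for whom the Controller log shows at least one patient dose attempt, whether or not a tablet was delivered or reached the mouth. Misplaced tablets belong in this set because a patient whose only tablet landed outside the mouth could otherwise be judged not to have received study drug and be lost in the same way.

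Count primary events from the Controller data, as Protocol 9.1 and SAP 2.1 state, and use the suspected technical failure eCRF only for reconciliation. List failures at set-up, before patient use, separately. Keep the treated population for pain, global assessment and safety endpoints.

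The cost is wording in two sections. Staff already observe the first dose (Protocol 6.1.3) and download the Controller after each patient's use (6.1.4). Two practical points need attention. The termination CRF is required only for patients who received study drug (4.4), so the plan must say that Controller files are retained for undosed patients. The sponsor should also confirm that the log records an attempt that ends in an error. The reported failure rate may be slightly less favourable, and the rates of unrequested or lockout dispenses and of misplaced tablets may be diluted by a negligible amount.
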